9.0 QUALITY CONTROL AND ASSURANCE

During and/or after completion of the study, quality assurance officers named by Novartis or the regulatory authorities may wish to perform on-site audits. The investigators will be expected to cooperate with any audit and to provide assistance and documentation (including source data) as requested.

Novartis representatives are responsible for contacting and visiting the investigator for the purpose of inspecting the facilities and, upon request, inspecting the various records of the clinical study (eg, CRFs and other pertinent data) provided that patient confidentiality is respected.

10.0 PLANNED STATISTICAL METHODS

This is a phase IIA activity trial of TKI258 for treatment of castrate resistant prostate cancer with skeletal metastases. The two primary outcomes are survival time and early response as characterized by a drop in PSA as defined by working group criteria. Based on historical mean survival time 8 months, a mean survival time on average > 10 months with TKI258 would be considered promising evidence of anti-disease activity. The planned sample size is 40 patients, with an anticipated accrual rate of 3 patients per month. Based on historical experience using carefully selected candidates with evidence for iliac involvement on bone scan, we anticipate that ~60% of patients will have positive biopsies. No early stopping rule in terms of the probability of PSA response will be employed because it is not known whether blocking the stromal-epithelial interactive pathway (SE-pathway) will be related to clinical benefit. Consequently, it may be the case that PSA does not drop but survival time is prolonged due to inhibition of disease progression by TKI258. Given the short survival time of these patients and anticipated accrual rate of 3 patients per month, it also will not be

feasible to implement an early stopping rule in terms of observed survival times. Based on an historical rate of 20% grade 3 or 4 toxicity with standard therapies the method of Thall and Sung (1998) will be used to monitor toxicity. Unadjusted survival time will be estimated using the method of Kaplan and Meier (1958) and the effects of the following four potential prognostic covariates: Inhibition of FGF signaling by bone marrow biopsy at 4 weeks, modulation of the bone markers (a) urinary NTX and (b) bone specific alkaline phosphatase, and baseline signature of FGF signaling in terms of FGF R-1, FGF R-3 and FGF 9 on Prob(PSA response) will be estimated using logistic regression, and on survival time will be estimated using the Cox model or an appropriate time-to-event regression model.

Preliminaries: This is a phase IIA activity trial of TKI258 for treatment of castrate resistant prostate cancer with skeletal metastases. The two primary outcomes are survival time and early response as characterized by a drop in PSA as defined by working group criteria (25).

Historical Experience and Goals: Based on the historical experience in which the mean survival time was 8 months, under a Bayesian model we assume that the unadjusted mean survival time with TKI258 follows an uninformative inverse gamma with mean 8 and variance 1000, equivalently with scale parameter 2.064 and shape parameter 8.512, denoted mE ~ IG(2.064, 8.512). A mean survival time on average > 10 months would be considered promising evidence of anti-disease activity. Formally, assuming that the historical mean survival mH ~ IG(52, 400), TKI258 will be considered promising if, based on the data from the trial, Pr(mE > mH | data) > .95. The planned sample size is 40 patients, with an anticipated accrual rate of 3 patients per month. In addition, the relationships between several potential prognostic covariates and the above clinical outcomes will be explored, as described below.

Monitoring Rules: No early stopping rule in terms of the probability of PSA response will be employed because it is not known whether blocking the stromal-epithelial interactive pathway (SE-pathway) will be related to clinical benefit. Consequently, it may be the case that PSA does not drop but survival time is prolonged due to inhibition of disease progression by TKI258. Given the short survival time of these patients and anticipated accrual rate of 3 patients per month, it will not be feasible to implement an early stopping rule in terms of observed survival times. However, based on an historical rate of 20% grade 3 or 4 toxicity with standard therapies, it will be assumed that p = Prob(grade 3 or 4 with TKI258) follows a beta prior with parameters (.20, .80). Using the method of Thall and Suung (26), based on the observed toxicity data, accrual to the trial will be stopped early if Pr(p > .20 | data) > .95, with this rule applied after successive cohorts f size 5. This rule says to stop the trial if [# patients with a grade 3 or 4 toxicity]/[# patients evaluated] is greater than or equal to 3/5, 5/10, 7/15, 8/20, 9/25, 11/30, 12/35. The operating characteristics of this rule are summarized in the following table.

True Prob(toxicity)	Prob(Stop Early)	Achieved Sample Size
		$25^{\text{th}}, 50^{\text{th}}, 75^{\text{th}}$ percentiles

.10	.01	40 40 40
.20	.11	40 40 40
.30	.47	20 40 40
.40	.86	5 15 25

Data Analysis. If the data on the 40 patients yield a sample mean of 10 months (the targeted 25% improvement) based on total follow-up time 400 months (all 40 deaths observed) then the posterior of m would be IG(42.064, 408.512), which has mean 9.95 months and posterior 95% credible interval 7.33 - 13.4 months. Similarly, if 35 deaths are observed with 5 death times administratively censored and total follow-up 460 months at the final analysis then the posterior of m would be IG(37.064, 468.512),), which has mean 13 months and posterior 95% credible interval 9.39 - 17.95 months. Unadjusted survival time will be estimated using the method of Kaplan and Meier (27). The effects of the following four potential prognostic covariates on Prob(PSA response) will be estimated using logistic regression (28), and on survival time will be estimated using the Cox model or, if the proportional hazards assumption is not satisfied, using an appropriate time-to-event regression model chosen based on preliminary goodness-of-fit analyses of the data (29). Each of the following covariates is a binary indicator.

- 1. Inhibition of FGF signaling by bone marrow biopsy at 4 weeks.
- 2. Modulation of the bone markers (a) urinary NTX and (b) bone specific alkaline phosphatase
- 3. Baseline signature of FGF signaling in temrs of FGF R-1, FGF R-3 and FGF 9.

Time of disease progression if defined by PSA alone is defined as follows: Three consecutive PSA elevations above nadir or baseline are required. Each increment in PSA should be a minimum of 1 ng/ml and at least 2 weeks apart or will not count. The time of PSA progression will be taken as the time of the first of these PSA elevations that represents an increment by at least 25% above the nadir or baseline. Given that increments in PSA do not always represent treatment failure, particularly when novel agents with uncertain effects on PSA levels are being evaluated, clinical and radiological correlation is recommended at the discretion of the treating physician. In patients with PSA progression alone without clinical or radiological evidence of disease progression, continued therapy on study is at the discretion of the treating physician in consultation with the principal investigator.

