TKI258 500mg PO daily for 5 days, followed by a 2 day rest period. Each cycle is 28 days.

Duration of Treatment:

Patients will continue to receive TKI 258 until progression, unacceptable toxicity or withdrawal of consent

Statistical Methods:

This is a phase IIA activity trial of TKI 258 for treatment of castrate resistant prostate cancer with skeletal metastases. The two primary outcomes are survival time and early response as characterized by a drop in PSA as defined by Prostate Cancer Working Group 2 criteria. Based on a historical mean survival of time 8 months, a mean survival time on average > 10 months with TKI258 would be considered promising evidence of anti-disease activity. The planned sample size is 40 patients, with an anticipated accrual rate of 3

patients per month. Based on historical experience using carefully selected candidates with evidence for iliac involvement on bone scan, we anticipate that ~60% of patients will have positive biopsies. No early stopping rule in terms of the probability of PSA response will be employed because blocking the stromal-epithelial interactive pathway (SE-pathway) may produce clinical benefit independent of PSA modulation. Consequently, it may be the case that TKI258 does not cause significant reductions in PSA, but survival time is prolonged due to inhibition of disease progression. Given the short survival time of these patients and anticipated accrual rate of 3 patients per month, it also will not be feasible to implement an early stopping rule in terms of observed survival times. Based on an historical rate of 20% grade 3 or 4 toxicity with standard therapies the method of Thall and Sung (1998) will be used to monitor toxicity.

Unadjusted survival time will be estimated using the method of Kaplan and Meier (1958) and the effects of the following four potential prognostic covariates Inhibition of FGF signaling by bone marrow biopsy at 8 weeks, modulation of the bone markers (a) urinary NTX and (b) bone specific alkaline phosphatase, and baseline signature of FGF signaling in terms of FGF R-1, FGF R-3 and FGF 9 on Prob(PSA response) will be estimated using logistic regression, and on survival time will be estimated using the Cox model or an appropriate time-to-event regression model.

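### Section 10 regresses PSA response on four binary markers by ordinary logistic regression in at most 40 patients; it names neither the model form nor the analysis set and has no provision for infinite odds ratios if PSA response is uncommon

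*Combined protocol and SAP*

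**What the plan says.** Section 10.0 (Planned Statistical Methods) names survival time and PSA response as the two primary outcomes and states "The planned sample size is 40 patients, with an anticipated accrual rate of 3 patients per month". On marrow sampling it says "we anticipate that ~60% of patients will have positive biopsies".

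The Data Analysis paragraph applies logistic regression to PSA response with four potential prognostic covariates and adds "Each of the following covariates is a binary indicator". The list is:

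- "Inhibition of FGF signaling by bone marrow biopsy at 4 weeks"
- "Modulation of the bone markers (a) urinary NTX and (b) bone specific alkaline phosphatase", which must count as two to make four
- "Baseline signature of FGF signaling in temrs of FGF R-1, FGF R-3 and FGF 9"

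No cut-points are given. The text does not say whether the covariates enter together or singly, which patients are analysed, how a missing marker is handled, or what happens if the likelihood has no finite maximum. The synopsis carries the same plan and allows that "it may be the case that TKI258 does not cause significant reductions in PSA".

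**The concern.** When all responders, or all non-responders, fall on one side of a binary marker or of a combination of markers, the data are separated. At least one maximum likelihood odds ratio is then zero or infinite, and the Wald interval printed by standard software means nothing. This becomes likely when responders are few relative to the number of covariates.

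The trial is small, and the plan accepts that PSA may not fall. The analysis serves a primary outcome, and relating PSA change to bone remodelling markers is a primary objective (section 2.1). A regression that cannot report an odds ratio would leave that question without an estimate. The unspecified analysis set adds a second risk: the bone markers need only urine and serum, but a joint complete-case fit would keep them only where the marrow markers also exist.

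**Working it through.** The plan gives no event count, power or precision for this regression, so it has no figure to reproduce.

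**Inputs from the documents**

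- N = 40 (section 10.0).
- Positive biopsies about 60% (section 10.0): 0.60 × 40 = 24 expected. The binomial 5th to 95th percentiles are 19 to 29.
- Four binary covariates (section 10.0, Data Analysis).
- TKI258 PSA response rate: not given. The only PSA response rate in the documents is 40% to 50%, for docetaxel-based regimens (section 1.2).

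**Assumptions of this check**

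Response of 10% to 50%; independent markers; marker prevalence 0.5 or 0.3; a common odds ratio per marker of 1, 2 or 3 (1 or 3 for single-marker models).

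**Expected responders**

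- n = 24: 24 × 0.10 = 2.4 and 24 × 0.20 = 4.8, that is 0.6 and 1.2 per covariate.
- n = 40: 40 × 0.10 = 4 and 40 × 0.20 = 8, that is 1 and 2 per covariate.

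**One marker at a time (exact; even split, no effect)**

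The estimate is not finite when any cell of the 2 × 2 table is empty. With response rate r, the two responder cells each have probability r/2. Empty non-responder cells are negligible here, so

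P ≈ 2(1 − r/2)^n − (1 − r)^n.

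- n = 24, r = 0.10: 2 × 0.2920 − 0.0798 = 0.504
- n = 24, r = 0.20: 2 × 0.0798 − 0.0047 = 0.155
- n = 40, r = 0.10: 2 × 0.1285 − 0.0148 = 0.242
- n = 40, r = 0.20: 2 × 0.0148 − 0.0001 = 0.029

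Simulation agrees: 51% to 52% and 14% to 16% at n = 24; 22% to 24% and 3% to 4% at n = 40.

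**Four markers jointly (simulation)**

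Each simulated data set was tested by linear programming for complete or quasi-complete separation, or a rank-deficient design. The first figure is for even splits and no effect. The bracket is the range over the prevalences and odds ratios above.

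| PSA response | n = 24 | n = 40 |
|---|---|---|
| 10% | about 77% (78–90%) | about 50% (49–72%) |
| 20% | about 39% (40–64%) | about 9% (8–27%) |
| 30% | about 16% (16–38%) | about 1–2% (1–8%) |
| 40–50% | about 4–7% (4–35%) | about 0% (0–7%) |

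Where a first figure lies just below its bracket, the difference is simulation error between runs. Over the range of assumptions, single-marker models give 50–60% at 10% response and 16–26% at 20% for n = 24, and 24–38% and 3–10% for n = 40. At 40–50% response they give 0–10% for n = 24 and at most 2% for n = 40.

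**Patients lost to the bone markers**

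If the fit were joint, complete-case and confined to biopsy-positive patients, 40 − 24 = 16 patients would leave the NTX and bone alkaline phosphatase estimates. Their intervals would be wider by about √(40/24) = 1.29.

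**Biopsy timing**

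The on-treatment biopsy is at 4 weeks in section 10.0, 8 weeks in the synopsis, and weeks 7 to 10 in section 7.4.5. Under an assumed exponential survival with the plan's 8-month historical mean, deaths before the biopsy would be 1 − exp(−0.92/8) = 10.9% by week 4 or 1 − exp(−1.84/8) = 20.5% by week 8. The expected 24 would become about 21 or 19. This loss is not built into the figures above.

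**The case against.** A reader might infer that the model is confined to at most 24 patients and will discard the other 40%. The documents do not support that. FGF R1 is studied in host as well as tumour cells (section 3.1), the objectives include FGF signalling in serum (section 2.0), the study title refers to marrow plasma, and the baseline signature names no specimen. Nothing excludes biopsy-negative patients, and 24 is an expectation, not a ceiling. Nor is the model said to be joint or complete-case; one marker per model, each in the patients who have it, fits the current text. The loss of 16 patients is therefore conditional on all three readings.

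A reader might also infer that the plan forecasts few PSA responders. It says only that PSA may not drop, as the reason for having no PSA stopping rule. At the docetaxel rate of 40% to 50%, ordinary logistic regression would usually work.

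The joint figures count any data set in which at least one coefficient diverges; the others may still be estimable. For a given marker in the joint model at n = 24, the chance is about 20% at 20% response (against about 39% for any marker) and 7% at 30% (against about 16%). At n = 40 and 20% response it is about 3%.

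Finally, the regressions are exploratory. The formal criterion for a promising result compares mean survival with its historical value and does not use them.

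All of this stands and limits the size of the point. It does not remove it: the response rate is unknown, low rates are within what the plan allows, and single-marker fits in all 40 patients can still fail.

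**Conclusion.** The point holds as a gap in specification with a foreseeable numerical failure. At PSA response of about 10% to 20%, ordinary maximum likelihood has a material chance of giving at least one infinite odds ratio: about 50% to 9% jointly and 24% to 3% singly with all 40 patients, rising to about 77% to 39% and 50% to 15% if only about 24 have readable markers. These figures assume independent, evenly split markers with no effect; less even splits or real effects mostly raise them. At 40% to 50% response the risk is small under most assumptions. The survival criterion and the estimate of the PSA response rate itself are unaffected.

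**What to change.** In section 10.0 and the synopsis:

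1. Fit the PSA-response regressions by Firth penalised likelihood with profile-likelihood intervals. In simulation this always gave finite estimates, with a mean log odds ratio close to the true value.
2. Estimate each marker's effect in every patient who has that marker, so that NTX and bone alkaline phosphatase use all treated patients with samples. Name the specimen for each FGF marker and say whether biopsy-negative patients have a value.
3. Make any joint four-marker model secondary, also by Firth, and report how many patients it uses.
4. Reconcile the biopsy week in section 10.0 with the synopsis and section 7.4.5.

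The cost is SAP wording and standard software. The single-marker effects are not mutually adjusted, which is a small loss with so few expected responders. Firth adds no information, so intervals will still be wide when responders are few.

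### The historical comparator IG(52, 400) has mean 7.84 months rather than the stated 8, and the words scale and shape for the TKI258 prior are transposed: two minor corrections to the survival rule

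*Combined protocol and SAP*

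**What the plan says.** The paragraph on historical experience and goals appears in the synopsis and again in Section 10.0. It starts from a historical mean of 8 months ("Based on the historical experience in which the mean survival time was 8 months"). The prior for mean survival on TKI258 "follows an uninformative inverse gamma with mean 8 and variance 1000", which the plan spells out as "equivalently with scale parameter 2.064 and shape parameter 8.512, denoted mE ~ IG(2.064, 8.512"). The comparator and the rule follow: "assuming that the historical mean survival mH ~ IG(52, 400), TKI258 will be considered promising if" the posterior probability that mE exceeds mH is greater than .95. The prose target is "A mean survival time on average > 10 months would be considered promising evidence of anti-disease activity".

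The Data Analysis paragraph of Section 10.0 then works two examples. With 40 deaths in 400 months, "then the posterior of m would be IG(42.064, 408.512"), with mean 9.95 and 95% credible interval 7.33 to 13.4. With 35 deaths in 460 months, the posterior is IG(37.064, 468.512), with mean 13 and interval 9.39 to 17.95. The same paragraph describes 10 months as a 25% improvement. No mean is printed for IG(52, 400).

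**The concern.** The rule on Pr(mE > mH) is the only formal efficacy criterion in the plan, since early stopping on PSA or on survival is expressly excluded. Its two ingredients should therefore match their descriptions.

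The comparator is meant to carry a historical mean of 8 months, and the 25% target makes sense only against 8, but its parameters give a slightly lower mean. That makes it a little easier to beat than the text says.

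The prior for TKI258 is described in words that contradict the mean and variance in the same sentence. A prespecified rule should not need the analyst to notice this and work out which part of the sentence to follow.

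**Working it through.** **Inputs.** All from Section 10.0: historical mean 8; TKI258 prior IG(2.064, 8.512) with stated mean 8 and variance 1000; comparator IG(52, 400); cut-off .95; 40 patients; the two worked posteriors.

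**Formulas.** For an inverse gamma with shape a and scale b, the mean is b/(a − 1) and the variance is mean²/(a − 2). With exponential survival, d deaths and total follow-up T, IG(a, b) updates to IG(a + d, b + T).

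**1. Order of the parameters, from the plan's own figures.**
- 2.064 + 40 = 42.064 and 8.512 + 400 = 408.512. Mean 408.512/41.064 = 9.95, interval 7.33 to 13.47. The plan prints 9.95 and 7.33 to 13.4.
- 2.064 + 35 = 37.064 and 8.512 + 460 = 468.512. Mean 468.512/36.064 = 12.99, interval 9.39 to 17.95. The plan prints 13 and the same interval.

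Deaths go to the first parameter and time to the second, so the notation is shape first.

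**2. TKI258 prior.**
- Shape 2.064, scale 8.512: mean 8.512/1.064 = 8.00; variance 8²/0.064 = 1000. Both agree with the text.
- As worded (shape 8.512, scale 2.064): mean 2.064/7.512 = 0.27 months; variance about 0.012. Neither agrees.

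**3. Comparator.** IG(52, 400): mean 400/51 = 7.843; variance 7.843²/50 = 1.23, SD about 1.11. The shortfall from 8 is 0.157 months, or 2%. Two neighbours with mean exactly 8 are IG(51, 400), 400/50, and IG(52, 408), 408/51.

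**4. The bar.** For independent inverse gammas, Pr(mE > mH) is the F distribution function with 2aE and 2aH degrees of freedom at (bE/bH)(aH/aE). For the first worked example the argument is (408.512/400)(52/42.064) = 1.26, giving .871; simulation gives the same. The bar is the T at which the probability equals .95 with 40 deaths, divided by 40. The chance of declaring promise at true mean μ is the probability that T, a gamma variable with shape 40 and scale μ, exceeds that value.

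| | IG(52, 400), as written | IG(51, 400) | IG(52, 408) |
|---|---|---|---|
| Comparator mean, months | 7.84 | 8 | 8 |
| T needed, months | 445.8 | 455.5 | 454.8 |
| Observed mean needed (T/40) | 11.14 | 11.39 | 11.37 |
| Chance of promise, true mean 8 | 1.2% | 0.8% | 0.8% |
| Chance of promise, true mean 10 | 22.7% | 18.6% | 18.9% |
| Pr(mE > mH), 40 deaths in 400 months | .871 | .849 | .850 |
| Pr(mE > mH), 35 deaths in 460 months | .990 | .987 | .988 |

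The bar shifts by 0.23 to 0.24 months. The first worked example fails the .95 rule and the second passes it, under every comparator.

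**The case against.** **The 7.84 is inferred and rounds to 8.** This is partly right. The plan attaches a mean of exactly 8 only to the TKI258 prior; for the comparator it gives parameters and, separately, a historical mean in whole months. The gap of 0.157 months is about one-seventh of the comparator's own SD (0.157/1.11 = 0.14). It is a mismatch with a repeated description, not a contradiction of a printed figure. It still calls for a correction. The same paragraph sets the TKI258 prior to three decimals so that its mean is exactly 8, and the 25% target is measured from 8.

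**The effect is small.** This stands. The bar moves by less than a quarter of a month, the chance of declaring promise at a true mean of 8 is about 1% either way, and no worked example changes verdict.

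**A stronger reading of the labels.** A reader might infer that the transposed words also change the bar. The documents do not support this. The stated mean and variance, the IG notation and both worked posteriors all use shape 2.064 and scale 8.512, so the rule as the plan operates it is unaffected. Coding the words for the TKI258 prior while keeping IG(52, 400) as shape 52 and scale 400 would mix two conventions. Applying the words to both would give the comparator a mean of 52/399 = 0.13 months, which would be noticed at once.

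**A stronger reading of the correction.** A reader might also expect a comparator of mean 8 to bring the rule into line with the 10-month target. It does not. An observed mean of 10 gives .871 as written and about .85 after correction. That gap comes from the .95 cut-off and the spread of both distributions, and the correction widens it slightly.

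**Conclusion.** Both errors are real and minor. On the plan's own convention the comparator has mean 7.84 months, 2% below the historical mean it represents. This lowers the bar from about 11.4 to 11.14 months and raises the chance of declaring promise by about 0.4 percentage points at a true mean of 8 and about 4 points at a true mean of 10. These figures assume exponential survival, independent distributions for the two means and all 40 deaths observed. They also assume that the comparator was meant to have a mean of 8, which the text implies but does not state. The transposed words make one sentence false and have no effect on the rule.

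**What to change.** Make these changes in both the synopsis and Section 10.0.

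1. Check the source data for the comparator. Then either replace IG(52, 400) with a distribution of mean 8, for example IG(51, 400) or IG(52, 408), or keep it and state that the historical mean used is 7.84 months. The documents do not show how 52 and 400 were obtained, so the choice belongs to whoever holds the historical data. Printing the mean of mH beside its parameters would settle the point.
2. Reword the description of the TKI258 prior as shape parameter 2.064 and scale parameter 8.512.

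The cost is one parameter or one added figure, plus the exchange of two words. If the comparator is changed, the bar rises by about 0.2 months, so the change should be made before the final survival analysis. No new data or change of design is needed.

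### The plan gives two different survival thresholds for calling TKI258 promising: a mean above 10 months in the prose, and about 11.14 months observed (40 deaths) under the formal rule

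*Combined protocol and SAP*

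**What the plan says.** Survival time is one of two primary outcomes. Under Historical Experience and Goals in Section 10.0, the plan first says: "A mean survival time on average > 10 months would be considered promising evidence of anti-disease activity". The next sentence makes this formal: "Formally, assuming that the historical mean survival mH ~ IG(52, 400"), followed by "TKI258 will be considered promising if, based on the data from the trial, Pr(mE > mH | data) > .95". The synopsis repeats both sentences in its own Historical Experience and Goals paragraph. The opening paragraph of Section 10.0 and the synopsis Statistical Methods paragraph give the 10-month statement without the formal rule.

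Data Analysis in Section 10.0 works two examples. In the first, the 40 patients "yield a sample mean of 10 months (the targeted 25% improvement"), "based on total follow-up time 400 months (all 40 deaths observed"). The second applies "if 35 deaths are observed with 5 death times administratively censored and total follow-up 460 months at the final analysis". Each gets a posterior, a posterior mean and a 95% credible interval. Neither gets a value of Pr(mE > mH | data).

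For toxicity monitoring the plan adds: "The operating characteristics of this rule are summarized in the following table". It gives no such table for the survival rule.

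**The concern.** One word, promising, is given two thresholds on a primary outcome, and the second is introduced as the formal version of the first. If they differ, a range of results exists for which the final report could say promising or not promising, each with support in the plan. A reader of the synopsis Statistical Methods paragraph or the opening of Section 10.0 alone would take 10 months to be the criterion. Because the survival rule has no operating characteristics, nothing in the plan shows how the rule behaves at the stated target.

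**Working it through.** **Inputs (Section 10.0).** Prior for the TKI258 mean: IG(2.064, 8.512), with stated mean 8 and variance 1000. Historical mean: IG(52, 400). Cutoff .95. Examples: 40 deaths with 400 months, and 35 deaths with 460 months.

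**1. Reproduce the plan's figures.** With the first parameter as shape a and the second as scale b, the mean is b/(a − 1) and the variance is b²/[(a − 1)²(a − 2)].
- Prior: 8.512/1.064 = 8.00; variance 1000. Both as stated.
- After d deaths and T total months, the posterior is IG(2.064 + d, 8.512 + T). This is the update for exponential survival, and it yields the two posteriors the plan prints.
- Example 1, IG(42.064, 408.512): mean 408.512/41.064 = 9.95; interval 7.33 to 13.47 (printed 7.33 to 13.4).
- Example 2, IG(37.064, 468.512): mean 468.512/36.064 = 12.99; interval 9.39 to 17.95 (as printed, with the mean rounded to 13).

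The plan attaches the words scale and shape the wrong way round: "equivalently with scale parameter 2.064 and shape parameter 8.512". Read literally, the prior mean would be 2.064/7.512 = 0.27. The plan's own posteriors use the numbers correctly, so this is a labelling slip.

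**2. Apply the formal rule.** If m ~ IG(a, b), then 1/m is gamma with shape a and rate b. With mE and mH independent,

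Pr(mE > mH | data) = F.cdf( ((8.512 + T)/400) × (52/(2.064 + d)); 2(2.064 + d), 104 ).

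| Deaths d | Months T | T/d | F argument | Pr(mE > mH) | Rule met? |
|---|---|---|---|---|---|
| 40 | 400 | 10.0 | 1.2625 | 0.871 | no |
| 40 | 420 | 10.5 | 1.3243 | 0.914 | no |
| 40 | 440 | 11.0 | 1.3861 | 0.943 | no |
| 40 | 446 | 11.15 | 1.4047 | 0.950 (0.9503) | yes |
| 35 | 460 | 13.1 | 1.6433 | 0.990 | yes |

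Two million simulated draws give 0.871 for the first row.

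**3. Solve for the bar.** Setting the probability to .95:
- d = 40: T = 445.75 months, 11.14 per death, posterior mean (8.512 + 445.75)/41.064 = 11.06. In whole months, 445 gives 0.9492 and 446 gives 0.9503.
- d = 35: T = 395.85 months, 11.31 per death. In whole months, 395 gives 0.9490 and 396 gives 0.9502.

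The bar per death depends on the number of deaths, so a single figure in months does not define it.

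**4. Try other readings of the 10-month statement and of the inputs.** Reading 10 months as the posterior mean (40 deaths, T = 402.13) gives 0.876. For 40 deaths and 400 months: mH fixed at 8 gives 0.911, mH fixed at 400/51 = 7.84 gives 0.932, and no prior on mE gives 0.896. None reaches .95.

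**5. Operating characteristics.** With exponential survival and all 40 deaths observed, total follow-up is Gamma(40, scale μ) for true mean μ. Pr(promising) = P(T > 445.75); the disagreement zone is 400 < T < 445.75.

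| True mean (months) | Pr(promising) | Pr(prose and rule disagree) |
|---|---|---|
| 8 | 0.012 | 0.053 |
| 10 | 0.227 | 0.252 |
| 11 | 0.446 | 0.259 |
| 12 | 0.659 | 0.198 |
| 13 | 0.815 | 0.123 |

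If the prose is read as a posterior mean above 10, the zone has probability 24%, 25% and 19% at true means 10, 11 and 12.

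The documents give no analysis date. Assuming analysis 6 to 24 months after the last entry, with 3 entries per month, simulation gives 19% to 22% at a true mean of 10 and 68% to 80% at 13.

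**The case against.** The best defence is that 10 months is a target and not a criterion. It appears under a heading that includes goals, it says on average, and Data Analysis calls it targeted. On that reading there is one operative rule, it is explicit and computable, and an analyst can apply it without ambiguity. This reading is possible, and the fix adopts it. But the plan does not say so. It uses promising in both sentences, joins them with the word formally, and in two places gives the 10-month statement alone. Even on this reading, the rule's 23% success rate at the target goes unreported.

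A reader might infer that the plan's own target result is promising by the prose and fails the rule. The documents do not support that: the prose requires more than 10, and the worked result has a sample mean of exactly 10 and a posterior mean of 9.95. The conflict lies in the zone above 10.

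A reader might also infer that the survival calculations are wrong or the rule invalid. They are not: the posteriors and their means reproduce, and the only numerical slip is an upper limit printed as 13.4 instead of 13.47.

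It is fair, too, that the trial is labelled exploratory, that its survival objective is estimation, and that no accrual or stopping decision uses this rule. Only the label in the final report is at stake, which limits the severity.

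**Conclusion.** The concern holds as an inconsistency in a decision threshold, and it should be fixed. With 40 deaths, observed means above 10 and up to about 11.14 months are promising by one sentence and not by the next. The threshold result depends only on the priors, update and cutoff as written. The 23% figure and the roughly one-in-four chance of landing in the disputed zone at true means of 10 or 11 rest on two further conditions. One is exponential survival, which the plan never names but its update implies. The other is that all 40 deaths are observed. The second is a best case for success at the targeted and higher means, since administrative censoring lowers the figures there. The bar of 11.14 is an observed cutoff and should not be read as the effect the trial is likely to detect: a true mean of 11.15 meets the rule only 48% of the time.

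**What to change.** Keep Pr(mE > mH | data) > .95, with mH ~ IG(52, 400), as the only definition of promising. Then:

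1. In both synopsis paragraphs and both places in Section 10.0, replace the 10-month statement with: *10 months is the targeted true mean survival, a 25% improvement over 8.* Cite the formal rule in the two paragraphs that now lack it.
2. State the bar as the T that solves the equation in step 2 of the working at .95 for d deaths, for example about 446 months at d = 40 and about 396 at d = 35.
3. Add Pr(mE > mH | data) to the worked examples: 0.87 (not promising) and 0.99 (promising).
4. Add Pr(promising) of .01, .23, .66 and .82 at true means 8, 10, 12 and 13, labelled *exponential survival, all 40 deaths observed*, with a note that administrative censoring lowers the figures at the targeted and higher means.
5. Swap the words scale and shape for 2.064 and 8.512, and correct the first upper credible limit to 13.5 (13.47).

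If the sponsor prefers 10 months as the bar, the rule must be changed to match and all these figures recomputed.

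The cost is wording, a formula and one four-row table, with no extra patients, visits or data. The downside is that the stated bar and the disclosed chance of success become less favourable.
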